#### Safety and Tolerability:

- Vital signs (heart rate [HR] and blood pressure [BP])
- Urine pregnancy tests for females of childbearing potential

## **5. STUDY METHODS**

### **5.1. General Study Design and Plan**

As background for the statistical methods presented below, this section provides an overview of the study design and plan of study execution. The protocol is the definitive reference for all matters discussed in what follows.

Approximately 40 subjects with either OAG or OHT will be randomized, for a target of 36 completed subjects. Subjects will be randomized in a 1:1 ratio to receive 1% Nyxol or placebo once daily for 14 days beginning at 8PM to 10PM on Day 1 and continuing through Day 14. Treatment-study IOP evaluations will occur on Days  $8 \pm 1$  Day and Day  $15 \pm 1$  Day. There will be Follow-up Visits on Day 16 at 8AM  $\pm 15$  minutes and by phone on Day 22 (7 days after the last Treatment-study Visit).

**ALL TREATMENTS WILL BE ADMINISTERED TO BOTH EYES AND IOP WILL BE MEASURED IN BOTH EYES.**

The eye with the higher IOP at the Qualification/Baseline Visit at 8AM is designated as the study eye. In the case where both eyes have the same IOP, the study eye will be the RIGHT eye. Baseline IOP evaluations will occur before dosing on Day 1.

If the subject meets all of the inclusion criteria and none of the exclusion criteria, including all three timepoint IOP measurements, this qualification visit becomes the Baseline Visit, a subject number is assigned, and he/she is randomized into the study.

Site personnel will demonstrate the proper instillation technique to the subject at the Qualification/Baseline Visit (Day 1) and the subject will self-administer a dose of artificial tears at the study site, instilling 1 drop in each eye from the unit-dose bottle (Note: if a drop is not instilled into the eye, the subject should wait approximately 10-15 seconds and administer a second drop). After successful instillation of the drop in each eye, the subject should carefully empty any remaining contents as directed.

The subject is given their study medication dropper bottles, and with instructions when to administer the eye drop (8PM to 10PM), and when to return to the clinic.

Each subsequent evening of dosing, the subject will administer one drop to each eye from a single new unit-dose bottle, then empty the remaining contents and store the opened bottle in the baggie provided and place it in the medication box for return to the study site at the Day 8 Visit. Each subsequent evening of dosing (approximately 24 hours between doses), the subject will follow the same procedures. At the Day 8 visit the medication box, complete with opened bottles and any unopened study medication, will be returned to the study site where the baggies of opened medication will be removed, and the study medication box will be re-dispensed with the unopened medication. During the second week of treatment, subjects will continue to administer one drop of study medication to each eye every night

using a new bottle for each dose, then emptying the remaining contents of that bottle and storing the opened bottles in the baggies and placing them back in the box to return to the study site at the Day 15 Visit. The Day 15 visit will be the last day of study treatment; no further study medication will be dispensed at this visit.

IOP measurements at the Baseline Visit and both Treatment-study Visits will be done at 8AM, 10AM and 4PM. All IOP measurements have a window of  $\pm 15$  minutes with at least 2 hours between the 8AM and 10AM assessments. IOP will be measured twice in both eyes at all time points. The mean IOP at each timepoint (8AM, 10AM, 4PM) is the average of the 2 IOP measurements at that timepoint. If the difference in the two IOP measurements is  $> 5$  mmHg, a third measurement will be obtained, and the three values averaged.

The lighting conditions will be kept the same from visit to visit. Every effort should be made to have the same clinician perform the IOP measurements at all timepoints and at all visits.

The schedule for assessments and timing of events is presented in [Table 1](#).

[REDACTED]

## 5.2. Inclusion – Exclusion Criteria and General Study Population

The general study population will include approximately 40 subjects at least 18 years of age and with OAG or OHT. The inclusion and exclusion criteria defined in the protocol apply to all subjects and are not repeated herein the SAP. Reference is made to the final protocol for the specific inclusion and exclusion criteria for study subjects.

## 5.3. Randomization and Blinding

All eligible and consented subjects will be randomized in a 1:1 ratio to receive 1 % Nyxol or placebo. Once a subject is qualified for the study (Qualification/Baseline Visit) the subject is assigned a randomization number.

Rules for unblinding a subject for safety reasons are fully described in the protocol and not repeated herein this SAP.

## 5.4. Analysis Variables

Variables to be summarized include demographics and baseline characteristics, medical (non-ocular) and ocular history, concomitant medications, and study drug accountability.

Efficacy variables include:

- IOP
- DCNVA (i.e., Near VA)
- BCDVA (i.e., Distance VA)
- Pupil diameter

Safety variables include:

- Conjunctival hyperemia (eye redness) measured with [REDACTED]  
[REDACTED]  
[REDACTED]  
[REDACTED]  
[REDACTED]  
[REDACTED]  
[REDACTED]  
[REDACTED]
- Biomicroscopy of anterior segment including evaluation of cornea, conjunctiva (other than redness) and anterior chamber. Fluorescein staining to be used.

- Ophthalmoscopy. Dilated fundus exam including optic nerve, macula, vessels and periphery.
- AEs
- Vital signs (HR and BP)
- Urine pregnancy tests for females of childbearing potential

## 6. SAMPLE SIZE

A sample size of 36 total completed subjects is needed for the study. Thirty-six completed subjects, who were originally randomized in a 1:1 ratio to the Nyxol 1% and the placebo groups,

additionally, it is assumed that there will be approximately 10% drop-out between Baseline/Day 1 and Day 15. To account for this drop-out, a total of 40 subjects will be randomized into the study.

## 7. GENERAL CONSIDERATIONS

### 7.1. Analysis Populations

The following analysis populations will be defined for this study.

#### 7.1.1. Full Analysis Set Population (FAS)

The FAS will include all randomized subjects who have received at least 11 doses of study medication without missing 2 consecutive doses and have both a Baseline and a Day 15 IOP measurement. The FAS will be used to analyze efficacy endpoints. Subjects included in the FAS will be analyzed as randomized.

#### 7.1.2. Per Protocol Population (PP)

The PP population will include all subjects in the FAS who had no major protocol deviations. The PP population will be used in confirmatory efficacy analyses. Subjects included in the PP population will be analyzed as randomized.

#### 7.1.3. All Randomized Population (AR)

The AR population will include all randomized subjects. This population is also known as the intent-to-treat (ITT) population. The AR population will be used in confirmatory efficacy analyses. Subjects included in the AR will be analyzed as randomized.

#### **7.1.4. Safety Population (SP)**

The Safety Population will include all randomized subjects who have received at least one dose of study medication. The Safety Population will be used to summarize safety variables. Subjects who are members of the Safety Population will be analyzed as treated.

#### **7.2. Covariates and Subgroups**

##### **7.2.1. Planned Covariates**

Planned covariates include baseline values for the given assessment.

##### **7.2.2. Planned Subgroups**

Subgroup analyses will be completed for all secondary efficacy endpoints related to IOP in those subpopulations with Baseline IOP in the study eye of  $<25\text{mmHg}$  and  $\geq 25\text{mmHg}$ . Subjects will be categorized as " $<25\text{ mmHg}$ " if their study eye Baseline IOP readings at all time points (8AM, 10AM, and 4PM) are  $<25\text{ mmHg}$ .

#### **7.3. Management of Analysis Data**

##### **7.3.1. Data Handling**

Data from unscheduled visits will not be included in the analysis of efficacy or safety, but will be listed.

##### **7.3.2. Missing Data**

The primary efficacy endpoint is the change from Baseline to Day 15 in mean diurnal IOP. For the analysis of the primary efficacy endpoint, observed case data will be used (no imputation will be performed for missing efficacy data) for the analysis using the FAS. However, confirmatory analyses will be performed using the AR population, with imputation performed for missing data as specified in [Section 7.3.2.3](#).

Otherwise there will be no substitutions made to accommodate missing data points for efficacy data. All data recorded on the case report form will be included in data listings that will accompany the clinical study report.

Safety data will be imputed in limited situations. If the severity of an AE is missing, then the severity will remain missing. If relationship of the AE to study drug is missing, the relationship will remain missing. Missing or partial dates for AEs or concomitant medications will be imputed as described in [Section 7.3.2.1](#). Otherwise, all summaries of safety endpoints will be completed using observed cases in the Safety population; no imputation will be completed.

### 7.3.2.1. Handling of Missing Date Values

#### Partial or Missing Dates

The following conventions will be used to impute missing portions of dates for adverse events and concomitant medications, if warranted. Note that the imputed values outlined here may not always provide the most conservative date. In those circumstances, the imputed value may be replaced by a date that will lead to a more conservative analysis.

#### A. Start Dates

- 1) If the year is unknown, then the date will not be imputed and will be assigned a missing value.
- 2) If the month is unknown, then:
  - i) If the year matches the first dose date year, then impute the month and day of the first dose date.
  - ii) Otherwise, assign 'January.'
- 3) If the day is unknown, then:
  - i) If the month and year match the first dose date month and year, then impute the day of the first dose date.
  - ii) Otherwise, assign the first day of the month.

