#### B. Stop Dates

- 1) If the year is unknown, then the date will not be imputed and will be assigned a missing value.
- 2) If the month is unknown, then assign 'December.'
- 3) If the day is unknown, then assign the last day of the month.

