#### **8.5. Prior and Concurrent Medications**

The number and percentages of all concomitant medications will be summarized by treatment group, Anatomical Therapeutic Chemical (ATC) level 4, and PT. The total number of concomitant medications and the number and percentages of subjects with at least 1 concomitant medication will be summarized by treatment group. All summaries will be performed using the Safety Population.

A concomitant medication is defined as any medication taken on or after the day of first exposure to study drug.

Prior medications are defined as any medication that has a start and stop date prior to the day of first exposure to any study drug, collected from up to 30 days prior to Screening.

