### **10.1. Adverse Events**

Adverse events will be coded using MedDRA, Version 22.0.

Treatment-emergent adverse events (TEAEs) are defined as any adverse event that begins or worsens after initiation of the investigational product and through the subject's last study visit (study completion or early termination) or follow-up telephone call. Serious adverse events will be recorded from the date of informed consent, throughout the clinical trial.

If the onset of an AE is on or after the date of first dose of study medication, or increasing in severity after first dose of study medication, then the AE will be considered treatment-emergent.

Only TEAEs will be summarized; all AEs (TEAE, non-TEAE) will be included in a by-subject listing.

The number and percent of subjects with any TEAEs will be summarized by system organ class and preferred term by treatment group and overall. At each level of tabulation (ex. at the preferred term level) subjects will be counted only once if they had more than one such event reported during the AE collection period.

Note that in MedDRA, ocular events are coded to the SOC of “special senses”. Thus, using SOC in the summaries will provide a separation of ocular and non-ocular adverse events.

The following summary tables will be presented for TEAE data:

- Overall summary of TEAEs
- Summary table of TEAEs by SOC and PT
- Summary table of TEAEs by highest relationship level to study drug by SOC and PT (not related, possibly related, related)
- Summary table of TEAEs by maximum severity by SOC and PT (mild, moderate, severe)
- Summary table of serious TEAEs by SOC and PT
- Summary table of TEAEs leading to withdrawal from the study by SOC and PT
- Summary table of TEAEs leading to study medication discontinuation by SOC and PT

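### The SAP's start-date imputation does not look at the stop date, so an adverse event that ended before the first dose can be counted as treatment-emergent, and a drug stopped before it can lose its prior status

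*SAP*

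**What the plan says.** SAP 7.3.2.1 introduces its date rules as follows: "The following conventions will be used to impute missing portions of dates for adverse events and concomitant medications, if warranted". Two start-date rules matter here.

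- Month unknown, rule A.2(i): "If the year matches the first dose date year, then impute the month and day of the first dose date".
- Day unknown, rule A.3(i): "If the month and year match the first dose date month and year, then impute the day of the first dose date".

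Rule B fills in partial stop dates, for example "If the day is unknown, then assign the last day of the month". No rule compares the start with the stop. The section adds a general override for cases where the imputed date is not the most conservative one: "the imputed value may be replaced by a date that will lead to a more conservative analysis".

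The imputed dates feed two classifications.

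- SAP 10.1 treats an event as treatment-emergent on this condition: "If the onset of an AE is on or after the date of first dose of study medication". Worsening after the first dose also qualifies. The stop date plays no part.
- SAP 8.5 defines a prior medication as "any medication that has a start and stop date prior to the day of first exposure to any study drug", and a concomitant one as taken on or after the day of first exposure.

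Protocol 9.3.4 uses a different test for prior medication: the end date alone, set against the date of randomization. SAP 3.3 reports no departure from the protocol's analyses.

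**The concern.** Setting an uncertain start to the first-dose date is a reasonable cautious choice when nothing else is known. It is not reasonable when a recorded stop date already shows that the event or drug ended before dosing. The rule then produces an impossible record, with a start after its stop, and the classification follows the impossible date.

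Such records can arise. Protocol 8.3 collects adverse events from consent, and Protocol 7.2.2 assesses them at the washout check. Protocol 6.2 records medications from 30 days before Screening. Under Protocol 7.2.2, treated subjects stop glaucoma drugs 28 to 35 days before Qualification, so their stop dates should often be known.

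What is at stake is the accuracy of the safety and medication tables. Adverse events are a primary safety measure (SAP 4.2.1), and only treatment-emergent ones are summarized (SAP 10.1).

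**Working it through.** The plan states no figure on this point, so there is nothing to reproduce. The check applies the rules as written.

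**Worked records** (assumed first dose 20 June 2019)

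| Record | Known start | Known stop | Imputed start | Result |
|---|---|---|---|---|
| (a) Adverse event | June 2019, day unknown | 10 June 2019 | 20 June 2019, by A.3(i) | Start 10 days after stop; treatment-emergent under SAP 10.1 |
| (b) Drug | 2019, month unknown | 20 May 2019 | 20 June 2019, by A.2(i) | Start 31 days after stop; fails the SAP 8.5 definition of prior |
| (c) Adverse event | May 2019, day unknown | 10 June 2019 | 1 May 2019, by A.3(ii) | Not treatment-emergent; correct |

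For record (b), SAP 8.5 gives no clean answer. Judged on its imputed start, the drug is concomitant. Judged on its recorded stop, it was not taken on or after first exposure, so it is in neither class. Protocol 9.3.4 makes it prior.

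**How often the rule misfires once a start date is partial**

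Assumptions: every first-dose date in 2019 (year inferred from the protocol and CRF dates in SAP 3.1); true start 1 to 35 days before first dose; fully known stop between the start and the day before first dose; all combinations weighted equally. The number of combinations is 365 × (35 × 36 / 2) = 365 × 630 = 229,950.

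- Day missing: 56,354 / 229,950 = 24.5% get a start on or after first dose.
- Month and day missing: 215,040 / 229,950 = 93.5%.
- With the imputed start capped at the known stop: 0 in both cases, and no start falls after its stop.

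**Washed-out glaucoma drugs**

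Assumptions: stop 28 to 35 days before first dose; true start up to 180 days before first dose. The combinations number 365 × (153 + 152 + … + 146) = 365 × 1,196 = 436,540.

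- Day missing, A.3(i): 86 / 436,540 = 0.02%.
- Month and day missing, A.2(i): 310,084 / 436,540 = 71%.

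For these drugs the risk therefore lies in the month-unknown rule with a start in the first-dose year. A drug started in an earlier year is handled correctly.

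These percentages count calendar combinations. They are not expected frequencies in the trial.

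**Size of one error.** 40 randomized 1:1 gives about 20 per arm, so one subject is 1/20 = 5 percentage points in a table row.

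**The case against.** The case against giving this much weight is substantial.

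- **Few records qualify.** An adverse event must start in the first-dose month, lack a start day and have a known pre-dose stop. The run-in is short, with a check at about two weeks, so an unknown start month is unlikely for an event. Protocol 7.2.3 sends adverse changes found at Qualification to the history form, and Protocol 13.2 queries omissions and discrepancies. This stands as a limit on frequency. It does not settle the partial dates that remain.
- **The SAP allows discretion.** Imputation applies only where warranted, and the override allows another date. This does not cure the problem. SAP 7.3.2 says partial dates will be imputed. The override is optional, leaves conservative undefined and does not mention the stop date. For an adverse event, counting it as treatment-emergent is arguably already the conservative direction.
- **A drug stopped before dosing was not taken on treatment, whatever its imputed start.** This is right, so concomitant status does not strictly follow from SAP 8.5. What remains is that the drug fails the SAP definition of prior, contrary to Protocol 9.3.4.

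A reader might also infer that a washed-out glaucoma drop would be handled as a prohibited medication, or that a resolved event would be attributed to study drug. The documents support neither. Major deviations come from the sponsor's blinded review (SAP 8.2), and all recorded CRF data, including the actual stop date, appear in listings (SAP 7.3.2). Relationship is assigned by the investigator (Protocol 8.3.1) and stays missing if not recorded (SAP 7.3.2). Treatment-emergent status describes timing only.

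**Conclusion.** The gap is real but small. As written, rules A.2(i) and A.3(i) can give a start later than a known pre-dose stop. SAP 10.1 then counts a resolved adverse event as treatment-emergent, and SAP 8.5 takes a stopped drug out of the prior class without clearly placing it elsewhere. Records with complete start dates, or with partial starts outside the first-dose month and year (or year), are unaffected.

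The consequence is confined to descriptive tables: Protocol 9.3.5 plans no statistical analysis of safety data. The efficacy analyses do not use these dates. It would go too far to claim bias between arms, because events and drug use that ended before dosing have no evident reason to differ by randomized arm. The number of affected records cannot be estimated from the documents and is probably small. The 5-point figure is the effect of one subject, not a forecast.

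**What to change.** 1. Add to SAP 7.3.2.1, rule A: the first-dose date is imputed only if the stop date is missing or falls on or after the first dose. Otherwise the imputed start may not be later than the stop date, with rule B applied first if the stop is partial. An event ending before the first dose is then not treatment-emergent on its onset date. Capping at the stop is safer than defaulting to the first of the month or 1 January, which could place an adverse event before consent although Protocol 8.3 collects events only from consent.
2. Align SAP 8.5 with Protocol 9.3.4, so that a drug with an end date before the first dose is prior. The cap alone does not cover a drug whose start year is unknown: rule A.1 leaves that start missing, and the drug cannot then be shown to meet a definition requiring both dates. By plan, randomization and first dose fall on the same day (Day 1), so using the first dose as the cut-off keeps the protocol's intent.

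Cost: one or two SAP sentences and one line of date-derivation code, with no change to data collection.

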#### B. Stop Dates

- 1) If the year is unknown, then the date will not be imputed and will be assigned a missing value.
- 2) If the month is unknown, then assign 'December.'
- 3) If the day is unknown, then assign the last day of the month.

### 7.3.2.2. Missing Baseline Data

Every effort will be made to ensure that accurate baseline information on the subjects is collected. In the event that a subject is missing baseline information the subject will be included in the safety population for assessment of safety, and excluded from the primary analyses. Each case of missing baseline data will be evaluated for potential inclusion in the exploratory endpoints. All baseline data will be observed cases, without imputation.

### 7.3.2.3. Imputation Methods

Imputation for efficacy data will only be performed for the confirmatory analysis of the primary efficacy endpoint, using the AR population. If 5% or fewer data are missing in all treatment groups, an analysis with last observation carried forward (LOCF) for missing data will be applied. If more than 5% of data in any treatment group are missing, multiple imputation will be employed to analyze incomplete data sets under the assumption that the mechanism responsible for the missing data is at worst characterized as missing at random (MAR).

Multiple imputation is a simulation-based approach where missing values are replaced by multiple Bayesian draws from the conditional distribution of missing data given the observed data and covariates, creating multiple completed data sets. These completed datasets can then be analyzed using standard analysis methods. Rubin (1987) presented rules for how to combine the multiple sets of estimates to produce overall estimates, confidence intervals, and tests that adequately incorporate missing data uncertainty.

Missing values for IOP will be imputed simultaneously based on an underlying joint normal distribution using a Markov Chain Monte Carlo (MCMC) method.

The imputations will be done separately for each treatment group and will include the following variables in the imputation model: IOP at Day 8 (8AM, 10AM, and 4PM) and Day 15 (8AM, 10AM, and 4PM). No imputation will be applied to the Baseline/Day 1 time points because those must be completed for the subject to meet the inclusion/exclusion criteria for study enrollment.

[REDACTED]

Example SAS code is provided below:

```
[REDACTED SAS CODE]
```

